Each participant will be asked to complete a baseline assessment (Visit 1), three-month follow-up (Visit 2), and a six-month follow-up (Visit 3). Longitudinal data will be analyzed, within language and within mode of administration (paper-based vs. talking touchscreen), on a scale-by-scale basis using multiple-group factor analysis to compare in Mplus software (see Table 3 schematic below). All items will be treated as categorical indicators with response categories collapsed if there are fewer than five responses for a given response option.

Table 3: Schematic of multiple-group confirmatory factor analysis to be used on a scale-by-scale basis			
	Visit 1	Visit 2	Visit 3
Adequate health literacy	Factor loadings/ IRT parameters	Factor loadings/ IRT parameters	Factor loadings/ IRT parameters
Low health literacy	Factor loadings/ IRT parameters	Factor loadings/ IRT parameters	Factor loadings/ IRT parameters

We hypothesize that a metric invariable model will fit well for the talking touchscreen method. Acceptable fit will be defined as $CFI \geq .90$, $TLI \geq .90$, and $RMSEA \leq .10$. We hypothesize that unacceptable fit indices will be obtained for the paper-based testing. For descriptive statistics, we will report all fit indices produced by Mplus as well as factor loadings for each item. Longitudinal data will also be used to develop new longitudinal DIF tools in R, but these results will be considered exploratory until they can be tried and tested in other data sets.

Study Populations

The study population includes medical patients and community member, all might which complete questionnaires in other clinical and research contexts, ages 18 and older.

Study Variables

Demographics

All demographic variables are described in the protocol. We will report descriptive statistics of all demographics within language group as well as in total. We do not have specific hypotheses about demographics, but may conduct and report analyses of them, as well as presented additional analyses of demographics based on requests from manuscript reviewers.

Health literacy and numeracy

HealthLiTT and the NUMI will be used to determine health literacy groups using the above-described cutoffs. HealthLiTT is our main health literacy variable. All analyses of the NUMI are secondary.

Health questionnaires

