Our exit interview serves multiple purposes. One purpose is to assess the testing experience for the participant. We hypothesize differences between the talking touchscreen and paper-based testing in terms of the testing experience. We will calculate Spearman correlations with 99% confidence intervals (CIs) for the three 5-point ordinal questions (see Exit Interview) and whether testing was talking touchscreen or not (coded 0/1). This nonparametric approach will determine which method of testing is more appropriate for people of low health literacy. CIs that do not contain zero will be regarded as statistically significant.

A second purpose of the exit interview is to gather data on how health literacy influences other areas of health. Specifically, we have included four questions about colorectal cancer screening to determine a person's level of adherence to published guidelines.

Meaning and purpose in life, defined as the pursuit of worthwhile goals and an accompanying sense of fulfillment and coherence in one's life,²⁶⁻³⁰ is recognized as a fundamental facet of psychological wellbeing and important determinant of both physical and mental health. Individuals who report greater meaning and purpose are more motivated to engage in their healthcare and improve their overall health and wellbeing. Research demonstrates that individuals who report greater meaning and purpose also endorse greater self-efficacy, or perceived confidence in the ability to manage one's health, and are more likely to participate in preventive health services, including cholesterol screenings, colonoscopies, mammograms, Pap smears, and prostate exams.³¹⁻³³ In the current study, we will examine the impact of meaning and purpose in life and health-related quality of life (i.e., anxiety, depression, fatigue, pain intensity and interference, physical function, sleep disturbance, and disruption of social roles and activities) on adherence to national guidelines for colorectal cancer screening. Colorectal cancer screening was assessed using the National Cancer Institute Health Interview National Trends Survey (HINTS).³⁴ Adherence will be defined as receipt of screening within recommended timeframes according

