to guidelines from the United States Preventive Services Task Force (USPSTF) in effect during the study years. For colorectal cancer, men and women ages 50 to 75 years old will be classified as adherent if they report receipt of either a fecal occult blood test (FOBT) within 1 year, colonoscopy within 10 years, sigmoidoscopy within 5 years, or both a colonoscopy and sigmoidoscopy within 10 years. Correlations will be conducted in order to examine bivariate associations among study variables, including meaning and purpose, health-related quality of life, and other relevant factors (i.e., age, gender, financial strain, education, race/ethnicity, language, and medical comorbidities). Primary analyses will be conducted using logistic regression to examine the relationship between meaning and purpose and health-related quality of life with adherence to national colorectal cancer screening guidelines (0 = non-adherence, 1 = adherence) when adjusting for relevant factors.

Exploratory analyses will include the calculation of a non-adherence risk score. That is, based on meaning and purpose and other covariates, we will determine a cutoff from (receiver operating characteristic) ROC curves derived from the logistic regression. Then, we will cross validate the cutoff using a subset of the data set aside and not used in the modelling. In both the training and testing data, we will calculate sensitivity and specificity and other prediction indices as a means to better identify individuals who may be at risk for not adhering to screening guidelines.

Interim and Final Analyses: Sleep as a mediator between depression and chronic pain

The follow analyses are an interim analysis to be conducted for the 2020 meeting of the International Society for Quality of Life Research (ISOQOL). These analyses will be conducted twice, once using all available data before the ISOQOL 2020 conference (21-24 October 2020, if the presentation is accepted and if the conference takes place), and again when data collection for the parent study has been completed. Thus, there is a planned interim analysis and a planned final analysis. The following analyses will be conducted within participants completing measures in English.

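### The colorectal-screening model leaves out health literacy, which the SAP gives as the reason for asking the questions, and its look-back outcome supports association only

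*SAP*

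**What the plan says.** All SAP text on this point is in the Exit Interview section unless another place is named.

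- **Purpose.** One reason for the exit interview is to "gather data on how health literacy influences other areas of health", and the four colorectal-screening questions are the example given. Protocol section 4.3 gives another reason: it links the questions to the Meaning and Purpose questionnaire, plans to relate adherence to answers on that questionnaire, and does not mention health literacy in that explanation.
- **Aim.** "we will examine the impact of meaning and purpose in life and health-related quality of life" on adherence to screening guidelines.
- **Outcome.** A person is adherent after "a fecal occult blood test (FOBT) within 1 year", or "colonoscopy within 10 years, sigmoidoscopy within 5 years, or both a colonoscopy and sigmoidoscopy within 10 years".
- **Model.** "Primary analyses will be conducted using logistic regression to examine the relationship between meaning and purpose and health-related quality of life with adherence". Adjustment is for relevant factors, listed one step earlier as "other relevant factors (i.e., age, gender, financial strain, education, race/ethnicity, language, and medical comorbidities". The list opens with *i.e.*, so it is closed. Neither Health LiTT nor the NUMI is in it.
- **Health literacy.** The section on health literacy and numeracy names Health LiTT as the main literacy variable.
- **Timing.** Under Study Timepoints, "Each participant will be asked to complete a baseline assessment (Visit 1), three-month follow-up (Visit 2), and a six-month follow-up (Visit 3". Meaning and Purpose is given at every visit. The exit interview is at Visit 3. The Protocol also allows the screening questions at one phone visit if they were not asked in person. The SAP does not say which visit's Meaning and Purpose score enters the model.

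**The concern.** Two things stand out.

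First, the SAP gives a literacy reason for collecting the screening data and then plans no analysis that contains literacy. Anyone following the plan as written would finish the primary logistic model without a health literacy coefficient. Literacy is also a plausible confounder. If it is related both to screening and to Meaning and Purpose scores, part of its effect will appear under meaning and purpose. Education and language would absorb some of this but need not absorb all of it. Elsewhere the SAP treats Health LiTT as distinct from education: the trauma-symptom regression (Aim 1) contains both, and the vaccine-confidence addendum makes literacy the mediator with education as a covariate.

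Second, the outcome looks back 1, 5 or 10 years from the interview, while the exposure is first measured nominally six months before it. A test done before the score was taken cannot have been caused by that score. The association could also run the other way, or reflect stable traits. That limits the conclusion whatever covariates are used.

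At stake is how a secondary result is read. A meaning-and-purpose finding could be reported as an effect on screening behaviour when it is partly a literacy difference, and the literacy question would remain unanswered.

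**Working it through.** The documents give no sample size, effect size or power for this analysis, so there is no figure of the plan's own to reproduce.

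**1. Covariates against purpose.** The seven listed factors are age, gender, financial strain, education, race/ethnicity, language and medical comorbidities. Health literacy is absent from these and from the variables named for the bivariate correlations. Health LiTT is collected at Visit 1, so it is available.

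**2. Share of each look-back window that precedes the score.** Inputs: windows of 12 months (FOBT), 60 months (sigmoidoscopy) and 120 months (colonoscopy, and both together), from the SAP. The gap is the time from the Meaning and Purpose score to the screening question. Share = 1 − min(gap, window)/window.

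| Score used, screening asked at | Gap (months) | Colonoscopy | Sigmoidoscopy | FOBT |
|---|---|---|---|---|
| Baseline, Visit 3 | 6 | 114/120 = 95% | 54/60 = 90% | 6/12 = 50% |
| Visit 2, Visit 3 | 3 | 117/120 = 97.5% | 57/60 = 95% | 9/12 = 75% |
| Same visit | 0 | 100% | 100% | 100% |
| Baseline, interview delayed to 12 months | 12 | 90% | 80% | 0% |

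Turning these into shares of tests needs the test dates and the mix of tests, which the documents do not give. If dates were uniform within each window, and a quarter of adherent people qualified by FOBT and the rest by colonoscopy, the share before baseline would be 0.25 × 50% + 0.75 × 95% = 83.75%. With FOBT only it would be 50%.

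**3. Effect of leaving out Health LiTT.** All inputs here are assumptions: 250 or 400 analysed people; no true meaning-and-purpose effect; literacy odds ratio for adherence 1.5 per SD; literacy-meaning correlation 0.1, 0.2 or 0.3; the listed covariates represented by one index correlated 0.5 to 0.7 with literacy (25% to about 50% of its variance). The logistic model contains meaning and purpose and the index, with or without literacy. The result is the share of simulated data sets in which meaning and purpose is significant at the two-sided 5% level.

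| Literacy-meaning correlation | N = 250, no Health LiTT | N = 400, no Health LiTT | With Health LiTT |
|---|---|---|---|
| 0.2 to 0.3 | about 5 to 9% | about 7 to 13% | about 5% |
| 0.1 | little inflation | little inflation | about 5% |

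A repeat simulation with 3,000 data sets per setting agreed within about one percentage point.

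**4. Size of the bias.** A large simulated sample (400,000) had only education in the model, assumed to correlate 0.5 with literacy. With literacy-meaning correlation 0.1 to 0.3 and literacy odds ratio 1.3 to 2.0 per SD, the meaning-and-purpose odds ratio was 1.02 to 1.17 per SD without literacy and about 1.00 with it. The true value was 1.00.

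**The case against.** The strongest reply is that the planned model does what Protocol section 4.3 announces: relate adherence to meaning and purpose. On that reading literacy was never the question, and education and language already serve as proxies. The analysis is also separate from the SAP's main DIF analyses.

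Much of this stands, and several stronger readings are not supported:

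- *The questions were added to study health literacy.* Only the SAP says so. The Protocol gives meaning and purpose as the reason. What the documents show is a conflict about purpose.
- *The model claims a causal effect.* The causal word is in the aim. The sentence defining the model speaks of a relationship.
- *Most qualifying tests happened before the exposure was measured.* The windows do not establish this. Window share is not test share, and for FOBT the share is 50% on the nominal schedule. It falls to 0% if a baseline score is paired with an interview 12 months or more later, which the Protocol's pandemic provisions make possible.
- *By the SAP's own account literacy drives both sides of the regression.* The SAP's link between literacy and Meaning and Purpose is a hypothesis about item parameters. It is not a stated difference in mean scores. Confounding is plausible but is an inference.
- *False-positive rates reach 20%.* That needs a model without the listed covariates, where the rate is about 10 to 20% under the same assumptions. The planned model adjusts for those covariates.

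The reply does not explain why the SAP states a literacy purpose in the same section and then leaves literacy out of every step of the screening analysis.

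**Conclusion.** The point holds in a limited form. As written, the SAP states a health literacy purpose for the screening questions and plans no estimate that addresses it. The omission also leaves a plausible confounder only partly controlled. The likely harm is modest: about 5 to 13% false positives in place of 5% at literacy-meaning correlations of 0.2 to 0.3, and little at 0.1. These rates rest wholly on assumed sample size, odds ratio, correlations and covariate overlap, none of which the documents give.

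Separately, the retrospective outcome confines the conclusion to association with past screening, whichever visit's score is used. The 95%, 90% and 50% figures assume a baseline score and an interview at six months.

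This affects a secondary analysis and does not touch the DIF hypotheses. It is worth acting on because the remedy is specific and nearly free.

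**What to change.** 1. Add continuous Health LiTT to the adjustment list and the primary logistic model, and report its coefficient with a confidence interval. If it is left out on purpose, say why.
2. Reconcile the purpose of the screening questions between the SAP's Exit Interview section and Protocol section 4.3.
3. State which visit's Meaning and Purpose score is used, and how interviews that were delayed or done by phone are paired with it.
4. In the aim, replace *impact* with association with past screening, in line with the model sentence.
5. Describe the exploratory ROC cut-off as classifying current adherence status.

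The cost is one covariate already collected, one extra model parameter and a few lines of SAP text. The conclusion becomes more modest.

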Using a large sample, we will determine the psychometric properties of health questionnaires across levels of health literacy. Testing will be conducted in English and Spanish, across two modes of administration (paper-and-pencil vs. talking touchscreen). Each participant will have three visits (baseline, 3-month, and 6-month follow-up), described below, in order to determine changes in psychometric properties over time. We will use *differential item functioning* (DIF) and other psychometric analyses to identify questionnaire items with varying characteristics across levels of health literacy. Before the COVID-19 pandemic, our original plan was to recruit $N = 1216$ participants for in-person assessments. At the time of this plan our final N is 728 participants who have completed a health literacy assessment; some of these participants are missing data on subsequent questionnaires. In-person recruitment was put on hold during the COVID-19 pandemic; in order to adapt the the pandemic, a subset of participants ($N = 304$) was invited to a phone-based protocol that included data collection about the impact of COVID-19, vaccine confidence, and health-related quality-of-life (PROMIS-29 profile).

- **Develop alternative modes of test administration that can better accommodate people with low health literacy.** National statistics indicate that 14% of adults in the United States have below basic reading skills, and over 75 million Americans have below basic or basic health literacy skills.¹⁴ These data strongly indicate that many individuals seeking health care will have difficulties with written questionnaires, even those that have been carefully developed such as those in the NIH PROMIS. We will test an alternative mode of administration that has been specifically designed to aid people of low health literacy – a computer-assisted “talking” version that uses speech technology that participants can privately access as needed to have items and response options

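### The exploratory non-adherence cut-off is checked on one set-aside subset of unstated size, and the SAP does not say whether the primary regression includes those people; resampling would be more precise

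*SAP*

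**What the plan says.** The SAP's Exit Interview section describes two analyses of colorectal screening adherence, in adjacent paragraphs.

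- **Primary.** "Primary analyses will be conducted using logistic regression to examine the relationship between meaning and purpose and health-related quality of life" with guideline adherence as a 0/1 outcome. The candidate adjustment factors are "age, gender, financial strain, education, race/ethnicity, language, and medical comorbidities". The outcome is defined by age: "men and women ages 50 to 75 years old will be classified as adherent" if they report one of the listed tests in time.
- **Exploratory.** "Exploratory analyses will include the calculation of a non-adherence risk score". For this, "we will determine a cutoff from (receiver operating characteristic) ROC curves derived from the logistic regression", and then "we will cross validate the cutoff using a subset of the data set aside and not used in the modelling". The reporting plan is: "In both the training and testing data, we will calculate sensitivity and specificity and other prediction indices".

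The following are not stated:

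- the fraction set aside, and how or when the subset is chosen;
- whether the check is repeated over different subsets;
- whether the primary regression uses all eligible people or only the training part;
- how many people are eligible, and what non-adherence rate is expected;
- any confidence interval for sensitivity or specificity.

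The only ceiling on the sample is in the SAP's Study Objectives: "At the time of this plan our final N is 728 participants who have completed a health literacy assessment". Under protocol section 4.3 the screening questions are asked at the exit interview of people aged 45 or older, or once by phone if not already answered in person. The eligible group is therefore smaller than 728 by an amount the documents do not give.

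**The concern.** A single hold-out spends data twice: the score is built on fewer people, and its accuracy is judged on fewer still. Sensitivity is estimated only among the non-adherent people in the test part, which may be a small group. The result also depends on which people happen to fall into it.

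There is an ambiguity as well. The cut-off comes from the logistic regression, and the only logistic regression described up to that point is the primary one. A team following the text literally could restrict the primary model to the training part, which would cost it precision. It could also score the test people with a model they had helped to fit, which would flatter the cut-off. One sentence saying who enters which model would settle this.

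At stake is whether the reported sensitivity and specificity are precise enough to judge if the score is useful, and whether the primary association analysis keeps all its participants.

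**Working it through.** The documents contain no figure to reproduce. All counts below rest on stated assumptions.

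**1. How many people carry the estimates.** Let N be the number eligible (aged 50 to 75 with screening answers), q the proportion non-adherent and h the fraction held out. Sensitivity rests on N × q × h people and specificity on N × (1 − q) × h. With q = .30 and h = 1/3:

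- N = 150: 150 × .30 / 3 = 15 non-adherent, and 150 × .70 / 3 = 35 adherent.
- N = 350: 350 × .30 / 3 = 35 non-adherent, and 350 × .70 / 3 ≈ 82 adherent.

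A wider grid starts from 728 with 60–100% having screening data, 30–60% aged 50 to 75, 20–50% held out and 20–50% non-adherent:

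- Eligible: 728 × .6 × .3 ≈ 131 to 728 × 1 × .6 ≈ 437.
- Test set: 131 × .2 ≈ 26 to 437 × .5 ≈ 218, median 73.
- Non-adherent in the test set: 5 to 109, median 25.

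**2. Binomial precision at a true sensitivity of .70.** SD = √(.21/n), and the 95% half-width is 1.96 × SD.

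- n = 15: SD .118, half-width .23.
- n = 35: SD .077, half-width .15.

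A middle case has 728 × .75 × .40 ≈ 218 eligible, 30% held out and 30% non-adherent, which gives 20 non-adherent and 46 adherent people in the test set. Observed values near .75 then have exact (Clopper-Pearson) 95% intervals of .51 to .91 for sensitivity and .59 to .86 for specificity.

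**3. Split against bootstrap optimism correction.** The SAP names 7 adjustment factors, meaning and purpose, and 8 quality-of-life domains. That is 16 coefficients before any multi-category coding. Simulations used 12 or 18 predictors, about 30% non-adherent and a one-third split. Root-mean-square error (RMSE) with 12 predictors, 4 of them real, over 200 datasets per N:

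| N | Split: sensitivity / specificity | Bootstrap: sensitivity / specificity |
|---|---|---|
| 150 | .124 / .078 | .078 / .046 |
| 250 | .089 / .061 | .055 / .037 |
| 350 | .081 / .053 | .048 / .031 |

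Across runs with 12 and 18 predictors, the split's RMSE for sensitivity is about .12–.14 at N = 150 and .08–.09 at N = 350. For bootstrap correction it is about .08–.09 and .05. For specificity the range is .05–.09 against .03–.05. The split figures agree with the binomial SDs in step 2, which are a floor for them. Bootstrap correction still overstated sensitivity by about 4, 3 and 2.5 points at N = 150, 250 and 350, and by about 2 to 5 points across runs.

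**4. What depends on the ambiguity.**

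- *If the held-out people are dropped from the primary regression:* standard errors rise by 1/√(1 − h), which is 12%, 20% and 41% for h = .20, .30 and .50. A test with 80% power falls to Φ[(1.96 + .842)√(1 − h) − 1.96] = 71%, 65% and 51%.
- *If the full-data fit scores the test people:* with 18 predictors, a 30% hold-out, a Youden cut-off and 600 runs, test-set Youden J averaged .352 and .324 (N = 218 and 273), against .175 and .187 in new people.
- *If the primary model uses everyone and the score is refitted on the training part only:* test-set J averaged .155 and .164, against .158 and .169 in new people. There is no leak, and nobody is lost from the primary model.

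**The case against.** - **The risk score is exploratory.** The SAP says so at the start of that paragraph, and its Overview promises to mark exploratory work clearly. No hypothesis or decision rule depends on the cut-off. This stands and limits the weight of the point.
- **A reader might infer a forced choice:** that the set-aside subset must either shrink the primary regression or leak into it. The documents do not support this. The two analyses are described separately, and nothing prevents a full-data primary fit alongside a training-only refit. Step 4 shows that this route avoids both problems.
- **A reader might infer that leakage is planned.** The SAP's own words are against it: the subset is kept out of the modelling, and training and testing data are named. What remains is silence about who enters the primary regression.
- **A reader might take the small test set as a documented fact.** It is not. The eligible number, the non-adherence rate and the split are all assumed, and the wider grid reaches 218 people in the test set.
- **Hold-out against bootstrap is partly a trade of variance for bias.** A clean hold-out avoids the residual optimism of bootstrap correction. That is true, but RMSE counts bias as well as variance, and bootstrap correction still does better at every N examined.

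**Conclusion.** The point holds as a low-severity refinement. The plan validates an exploratory cut-off on one subset of unspecified size, gives no interval for its accuracy, and leaves open whether the primary logistic regression includes the held-out people.

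If 150 to 350 people are eligible, about 30% are non-adherent and one third are held out, sensitivity would be estimated from about 15 to 35 people. Its error would be roughly one and a half times that of bootstrap correction (for example .124 / .078 = 1.6 at N = 150 and .081 / .048 = 1.7 at N = 350). The ordering was the same at every N and with both numbers of predictors. The exact sizes depend on the assumed effect sizes and counts, and a much larger eligible group would narrow the gap in absolute terms.

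The losses in step 4 are conditional on how the text is implemented. They are a reason to clarify it, not evidence that either would occur.

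**What to change.** Amend the Exit Interview section of the SAP as follows:

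1. State that the primary logistic regression uses all eligible participants.
2. Develop the score and cut-off on all of them. Validate by bootstrap optimism correction or repeated 10-fold cross-validation, repeating both the model fitting and the choice of cut-off in every resample.
3. Report corrected sensitivity, specificity and AUC with intervals, together with the number eligible and the number non-adherent.
4. If a hold-out is kept, give its fraction and how it is drawn. Fit the score and choose the cut-off on the training part only, separately from the full-data primary model, and give intervals for the test-set results.

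The cost is SAP wording, a short loop in R and a little more computing; no new data are needed. The downsides are that there is no physically separate test set to show readers, and that a small residual optimism remains (about 2 to 5 points of sensitivity in simulation), which the report should acknowledge.
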